SPM production occurs via stereospecific conversion of essential fatty acids, including eicosapentaenoic acid (EPA), n-3 docosapentaenoic acid (DPA) and docosahexaenoic acid (DHA) by leukocyte enzymes, primarily lipoxygenases and cyclooxygenases. The omega-3 derived SPM are divided into four main families D- and E-series resolvins (Rv), protectins (PD) and maresins (MaR) and display both overlapping as well as characteristic biological actions. Each actively limits further neutrophil recruitment to the site of inflammation (1-3), they reduce chemo-attractant production and adhesion molecule expression, counter-regulate the production of pro-inflammatory mediators by regulating their formation and clearance, and promote neutrophil apoptosis and their clearance by macrophages as well as pain. In addition the maresins actively promote the repair and regeneration of damaged tissues, the protectins display potent anti-viral actions the D-series resolvins regulate B-cell antibody production and the E-series resolvins regulate T-cell and dendritic cell responses (1-3).

Studies investigating the production of these molecules during unresolved or chronic inflammatory conditions in experimental settings demonstrate that dysregulation in SPM production may be an underlying cause for disease propagation. For example in delayed or non resolving *Escherichia coli* infections SPM production becomes dysregulated leading to exacerbated local and systemic inflammation, failure of the host response to clear the invading pathogen and eventually death. Results with human tissues lend further support to this hypothesis, where SPM production is found to be dysregulated in a number of clinical settings including Alzheimer's disease and sepsis.

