8.7 Experimental Methods

After collection samples will be processed William Harvey Centre for Biochemical Pharmacology/Clinical Pharmacology Laboratories within one hour of following standard operating procedures listed in the *Lipid Mediator Unit Laboratory Manual*.

White Blood cell phagocytosis of Escherichia coli:

- 20 µl of blood will be incubated with 2×10^7 C.F.U. of fluorescently labeled E. coli

- Cells will be incubated at 37°C for 1h
- Cells will then be processed for flow cytometry using established protocols
- The extent of phagocytosis will be assessed using flow cytometry

Peripheral blood cell activation

- 20µl of whole blood will be incubated with or without 100µM of PAF for 1h at 37°C
- Cells will be washed 2x with PBS containing 5% fetal calf serum
- Cells will then be incubated with the following fluorescently conjugated antibodies for 15 min at room temperature
- Cells will then be processed for flow cytometry
- Adhesion molecule expression as well as platelet-leukocyte aggregates will be assessed using flow cytometry

Lipid mediator profiling

- Plasma (2ml) will be placed in 8 ml of ice-cold methanol containing deuterium labeled internal standards
- Samples will be stored at temperatures of -80°C
- Samples will be processed in batches of 20-24.
- Here samples will be centrifuged at 3000xg for 10 min at 4°C
- Supernatants will be collected
- Lipid mediators (LM) will be extracted using solid phase extraction techniques
- Isolated LM will be profiled using liquid chromatography tandem mass spectrometry (see ref 17)
- At the end of the study any excess or unused samples will be disposed of unless written consent is obtained from participant for longer term storage. Sample disposal will be conducted following standard operating procedures as outlined in the Biochemical Pharmacology laboratory manual.

RNA storage

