9.3 Sample Size

Power calculations were conducted using data obtained from published studies where healthy volunteers were given 1 mg essentially (from a different source to that being investigated in the present study) and peripheral blood lipid mediator levels were evaluated pre-essential fatty acid and 4 hours after supplement intake (Colas et al Reference 17). Using pre and post values of 10 mediators values from these studies and Wilcoxon matched-pairs signed rank test a sample size of 33 participants is required to detect a threefold odds of an increase in post value when compared with the pre value with a power of 80% at the 5% level of statistical significance using the formulae from reference 18. Fifty mediators will be examined and it is recognized that at the 5% level of statistical significance around 2-3 mediators will falsely be identified as having significant changes. However the functional effect of all significant mediators will be subsequently examined by assessing white blood cell function, including the ability of peripheral white blood cells to phagocytose bacteria and the response of peripheral white blood cells and platelets to an inflammatory stimulus. If we do not observe increases in the ability of peripheral white blood cells to phagocytose bacteria and/or decreases in the activation of peripheral white blood cells and platelets then these mediators will be assumed to be false positive results. For these analysis the white blood cell function and peripheral blood lipid mediator levels at the 2h and 4h intervals post essential fatty acid/placebo administration will be compared to pre-supplementation values. The time point and dose that give the greatest change in all the mediators and the greatest regulation of peripheral white blood responses will be judged to be the main outcome measure for future trials.

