9.4 Statistical Analysis Plan

Wilcoxon matched-pairs signed rank test will be used to analyse the pre and post values of 10 mediators as well as white blood cell function (at 2 and 4h). The time point corresponding to the greatest number of the mediators being statistically significantly different from their pre-test values at the 5% level of statistical significance will be identified as the time point of interest. At the 5% level of significance testing 50 mediators will result in at least 2-3 associations being falsely statistically significant. Thus, the functional effect of all significant mediators will be subsequently examined by assessing white blood cell function, including the ability of peripheral white blood cells to phagocytose bacteria and the response of peripheral white blood cells and platelets to an inflammatory stimulus to determine if the identified associations are likely to be true changes. If we do not observe increases in the ability of peripheral white blood cells to phagocytose bacteria and/or decreases in the activation of peripheral white blood cells and platelets then these mediators will be assumed to be false positive results. Values at different times will not be compared just the value at each time point will be compared to the same person's pre test values.

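### Section 9.4 picks the time point of interest by a count of significant mediators with no reference for what that count does by chance, and wrongly gives the expected 2.5 false positives as a minimum

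*Combined protocol and SAP*

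**What the plan says.** Section 9.4 tests each mediator's post value against the same person's pre value with the Wilcoxon signed-rank test at 2h and 4h. It then selects a time point by counting: "The time point corresponding to the greatest number of the mediators being statistically significantly different from their pre-test values", at the 5% level, becomes the time point of interest.

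On chance findings, section 9.3 says that "around 2-3 mediators will falsely be identified as having significant changes". Section 9.4 hardens this to "testing 50 mediators will result in at least 2-3 associations being falsely statistically significant". Both sections use the figure to justify a follow-up check: if white-cell function does not move in the expected direction, the significant mediators are taken to be false positives.

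Neither section mentions dependence between mediators, a chance distribution for the count, a minimum count or margin for selection, or a comparison with the placebo cycle's count. Section 9.4 refers to both 10 and 50 mediators.

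**The concern.** A count of significant results is a reasonable way to rank time points only if one knows how far it moves when nothing is happening. The plan gives an expected value, worded as a minimum, and nothing about spread.

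Spread matters here because the mediators are unlikely to behave independently. All are read from one extract per sample (section 8.7: "Plasma (2ml) will be placed in 8 ml of ice-cold methanol containing deuterium labeled internal standards"), and section 5.2 describes the pro-resolving mediators as made from a few fatty acids "by leukocyte enzymes, primarily lipoxygenases and cyclooxygenases". If changes are correlated, false positives tend to arrive together or not at all. The average stays the same, but large counts and large gaps between 2h and 4h become more common. A time point could then be named on one chance cluster.

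**Working it through.** **Inputs from the documents.** 50 mediators (9.3, 9.4); 5% level per test (9.3, 9.4); signed-rank test of post against own 0h value, at 2h and 4h (9.4); one 0h sample per cycle (7.4); 40 participants (8.3).

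**Assumptions.** The documents give no correlation between mediators, so equal correlation of 0 to 0.7 is assumed, with one family structure as a variant. Sidedness is not stated; two-sided tests are assumed.

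**Step 1: the plan's own figure.** Expected false positives = 50 x 0.05 = 2.5. This reproduces the figure in 9.3, and it holds under any correlation.

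**Step 2: is it a minimum?** With independent tests the count is Binomial(50, 0.05):
- P(0) = 0.95^50 = 0.077
- P(1) = 50 x 0.05 x 0.95^49 = 0.202
- P(0 or 1) = 0.279
- P(2 or 3) = 0.481
- P(10 or more) = 0.00016

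So the count falls below 2 in 28% of cases and equals 2 or 3 in only 48%. This needs no assumption about correlation beyond the case most favourable to the plan.

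**Step 3: how dependence widens the count.** Var(count) = 50 x 0.05 x 0.95 x (1 + 49r) = 2.375 x (1 + 49r), where r is the average correlation between the significant/not-significant indicators. At r = 0 the SD is 1.54. An SD of 2.7 needs only r = (2.7^2/2.375 - 1)/49 = 0.042.

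**Step 4: simulation with no true change.** 50 signed-rank tests per time point, with 2h and 4h sharing one 0h sample. The mean count stays at about 2.5 throughout.

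| Assumed correlation | 0 | 0.1 | 0.3 | 0.5 | 0.7 |
|---|---|---|---|---|---|
| SD of the count | 1.5 | 1.7 | 2.7 | about 4 | about 6 |
| No false positives | 8% | 10% | 19% | 36% | 56% |
| 10 or more, one dose and time | 0.02% | 0.2% | 2.6% | 6% | 8% |
| 2h and 4h counts differ by 5 or more | 3% | 4% | 13% | 20% | 23% |

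The second row is from runs with 33 participants; runs with 40 were nearly identical.

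**Step 5: variants.**
- Five families, correlation 0.5 within and 0.1 between: 10 or more in about 1-2%.
- Counting only false increases: 10 or more in 1.4%, 2.9% and 3.6% at 0.3, 0.5 and 0.7, about half the table's values.
- Only 10 mediators tested: the mean is 10 x 0.05 = 0.5; at correlation 0.5, counts of 6 or more occur in 0.6%, and 2h-4h gaps of 5 or more in 1.3%.

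**Step 6: role of the shared 0h sample.** Simulated with a shared and with separate 0h samples, the SD of the count at one time is 1.52 against 1.53 (correlation 0) and 4.03 against 3.99 (correlation 0.5). Sharing therefore causes no clustering within a time point. It only links the 2h and 4h counts (correlation about 0.1 to 0.2 instead of 0), so agreement between the two times is not independent confirmation.

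**The case against.** **The plan does not test the count against 2-3.** A reader might infer that 9.4 treats anything above 2-3 as real. It does not: the count only ranks time points, and the 2-3 figure leads into the white-cell check. This objection stands. What remains is that the ranking has no chance reference at all.

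**There is a safeguard.** The white-cell check exists, and 9.3 bases the choice for future trials on the size of the mediator changes and the white-cell responses, not on the count. But the check is one gate for all significant mediators together, with its two criteria joined by and/or. It cannot separate true from false within a cluster, and it does not calibrate the count that selects the time point in 9.4.

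**The common 0h sample.** It is tempting to blame it for clusters. Step 6 shows that it does not produce them; each mediator also has its own 0h value, and a new sample is drawn each cycle.

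**Larger figures across doses.** Taking the largest count over three doses and two times gives 10 or more in roughly 14-15% of trials at correlation 0.3 and 29-30% at 0.5. Section 9.4 has no rule comparing counts across doses, so these figures do not describe the plan.

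**The study is exploratory.** The synopsis says so, which limits the consequences. Section 9.4 nevertheless sets a 5% level and a named selection rule.

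**A permutation does not show which time is better.** This is correct. In 100 simulated trials with identical effects at both times (0.5 SD, correlation 0.3), a sign-flip gate passed 99%, yet the counts still differed by 5 or more in 63% of those. The fix must state this limit.

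**Conclusion.** The point holds in a limited form. Two things are established. First, the wording in 9.4 is wrong as a minimum, whatever the correlation. Second, the count that selects the time point has no chance reference, and ignoring dependence matters if mediator changes are at least moderately correlated.

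The size of the second part rests on an assumed correlation and on 50 mediators being tested. At 0.1 or below it is small. From about 0.3 upward, a gap of 5 or more between the 2h and 4h counts arises with no effect in about one trial in eight (13%) to nearly one in four (23%). With 10 mediators it largely disappears.

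The documents do not support saying that the plan judges counts against 2-3, that it lacks any safeguard, or that the shared 0h sample creates clusters. The change should be made because it is cheap and the count drives a named selection.

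**What to change.** 1. Reconcile 10 and 50 mediators in 9.3 and 9.4, and state the number tested.
2. In both sections, describe 2-3 as the average per set of 50 tests, and add that the number in one data set varies widely when mediators are correlated.
3. Report each count against a participant-level sign-flip permutation. Flip the sign of a participant's whole set of post-minus-pre differences (all mediators, both times together), about 10,000 times. Use the maximum count over the time points compared, and name no time point of interest if the observed count is within the chance range, for example at or below the 95th percentile.
4. Show the placebo-cycle count beside it. Sign-flipping does not remove diurnal change, which section 7.4 says is unknown.
5. State that exceeding the chance range shows that something changed, not that one time point is better than the other.

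**Cost.** SAP wording and a short program, with no new samples or participants. The permutation assumes joint symmetry of the differences, slightly more than each signed-rank test needs alone. In a limited check (300 runs), its size at a nominal 5% was 3% at correlation 0.3 and 5% at 0.6. Some counts will look less impressive than they would without a reference.

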7.4 Study Design / Plan – Study Visits

This is an open label double-blind, placebo controlled, crossover study that aims to determine the dose of omega-3 fatty acids that leads to an increase in peripheral blood SPM levels and the kinetics of this regulation.

- Each participant will give a baseline blood sample then they will be given one of the randomly allocated three doses of fish oil supplement, or a matching placebo in one of 8 study groups [this will be on a 1:1:1:1:1:1:1:1 ratio]. Blood will be collected again at 2h, 4h, 6h and 24h after supplementation/placebo.

- This design allows to compare the levels of SPM pre and post supplementation and therefore to account for inter participant variation in circulating SPM levels as well as for any differences in white blood cell responses *ex vivo*.

- Using a crossover design and a placebo, diurnal variation in the levels of SPM (currently not known) will be checked. In addition, using each volunteer as their own control for comparison with each dose of supplement will further improve the power of the study.

- Each participant is expected to be involved in the study for a maximum of 11 weeks from initial consent and screening.

- Participants will be asked to refrain from consuming caffeine containing drinks at least 2h prior to their visit.

- Participants will be expected to refrain from alcohol intake for at least 24h before screening for the study, and for at least 24h before each cycle of the study.

- Participants will also be asked not to take other supplements, medications for the duration of the study, and to avoid fish containing meals for 2 days before each study cycle.

- For each cycle, the participants will make two visits, the first visit will be of a maximum of 8hrs. Here baseline (0hrs) blood sample will be obtained and the supplement/placebo given.

- Blood will be collected 2hrs, 4hrs and 6hrs following supplement/placebo intake and the participant will be free to leave after the 6hrs blood collection.

- During this time participants will be asked to refrain from drinking caffeine containing drinks such as coffee or tea.

- Participants will then be asked to return the next day (24h after fish oil supplement/placebo intake).

[figure not shown]
- The 24h blood draw should take a maximum of 30 min.

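### The rules that select a time point and dose have no 'none identified' outcome, and a failed white-cell check does not withdraw the selection

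*Combined protocol and SAP*

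**What the plan says.** Section 9.4 compares 2 h and 4 h values with each participant's own pre-dose value by Wilcoxon signed-rank tests. "The time point corresponding to the greatest number of the mediators being statistically significantly different from their pre-test values at the 5% level" then "will be identified as the time point of interest". No condition is attached.

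Section 9.3 adds a second rule, which covers dose as well: "The time point and dose that give the greatest change in all the mediators and the greatest regulation of peripheral white blood responses" becomes the main outcome measure for later trials. This rule has no condition either.

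Both sections recognise false positives. Section 9.4 says that "testing 50 mediators will result in at least 2-3 associations being falsely statistically significant". Both answer this with the same check: if phagocytosis does not rise and/or activation does not fall, the significant mediators are treated as false positives. The check speaks of mediators only, not of the time point or dose.

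On the number of mediators, section 9.3 says "Fifty mediators will be examined", while the testing sentence in 9.4 refers to 10. Section 7.4 says that the study "aims to determine the dose of omega-3 fatty acids that leads to an increase in peripheral blood SPM levels", which is a question about whether an effect exists as well as where it is largest.

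**The concern.** Both rules are maxima. A maximum ranks the candidates, and does not ask whether the best of them differs from nothing. Section 9.4 predicts two or three chance findings among 50 mediators, yet never requires the winning count to exceed that. The 2 h and 4 h values are not to be compared with each other, and no contrast with the placebo cycle enters either rule. Nothing else in the selection step therefore supplies the missing test.

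At stake is the recommendation carried into later trials. If the plan is followed exactly, a time point can be reported as of interest for a supplement that does nothing. If the white-cell check then fails, the plan leaves open whether that time point still stands.

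**Working it through.** **Inputs from the documents.** 5% level per test, unadjusted (9.3, 9.4). Number of mediators m = 50 (9.3, 9.4) or 10 (9.4). Two time points, 2 h and 4 h, each against the same baseline. Three active doses plus placebo in a crossover, 40 participants planned (8.3) and 33 required (9.3).

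**Assumptions, not in the documents.** Tests are two-sided. Correlation between mediators is 0 to 0.6. The number of white-cell readouts is 2, with 6 as an alternative.

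**1. The plan's own figure.** 50 × 0.05 = 2.5, so two or three false positives is right as an expected number. It is not a minimum, despite the wording in 9.4: with independent mediators, P(2 or more) = 72% and P(3 or more) = 46%.

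**2. The 9.4 rule with no true effect, one dose, independent mediators.**
- The two counts each follow Binomial(m, 0.05). One time point leads strictly with probability 1 − Σ P(count = k)².
 - m = 50: 1 − 0.187 = 0.81.
 - m = 10: 1 − 0.463 = 0.54.
- At least one significant result over both times:
 - m = 50: 1 − 0.95^100 = 0.994.
 - m = 10: 1 − 0.95^20 = 0.64.

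The other outcomes are ties, including 0-0. For these the rule is undefined, which is different from concluding that no time point was found.

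**3. The same with a shared baseline and correlated mediators** (simulated signed-rank tests, n = 40, one dose):

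| Mediators | Correlation | Single time point named | Any significant result |
|---|---|---|---|
| 50 | 0 | 80% | 99% |
| 50 | 0.3 | 81% | 96% |
| 50 | 0.6 | 72% | 77% |
| 10 | 0 | 52% | 63% |
| 10 | 0.3 | 47% | 56% |
| 10 | 0.6 | 39% | 42% |

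Repeat runs with n = 33 or 40 gave 69-84% for 50 mediators and 36-52% for 10. Together with the exact values, that is roughly 70-83% and 35-54%. At a correlation of 0.9 the figures fall to 35% and 24%.

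**4. The 9.3 rule.** It uses no test, so each of its two maxima (mediators, white cells) exists in any dataset. Naming one cell requires both to fall in the same cell. With 3 doses × 2 times = 6 cells and unrelated measures, that happens by chance in about 1/6 = 17% of null trials; simulation gave 15-17%.

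**5. If the white-cell check were a veto, which is not written.** Suppose a significant favourable change is required, with probability 0.025 per test under no effect, and treat the tests as independent:
- 2 readouts × 2 times: 1 − 0.975^4 = 9.6%.
- 2 readouts × 6 cells: 1 − 0.975^12 = 26%.
- 6 readouts × 6 cells: 1 − 0.975^36 = 60%.

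Simulation with 50 mediators at correlation 0.3 gave about 10%, 25% and 57% of null trials in which a time point survives. If a favourable direction is enough, with 2 readouts, one survives in 84% (one dose) to 99.7% (three doses).

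**The case against.** The strongest reply is that a null route already exists. Section 9.4 applies the Wilcoxon test to white-cell function as well as to mediators. If function does not change, all the significant mediators are reclassified, and a time point defined only by counting them loses its basis. Read as a veto that needs a significant favourable change at the named time, with two readouts, n = 33 and white cells unrelated to mediators, the check cuts the null rate to 1-5% for one dose. A reader might infer that the plan cannot separate an active from an inactive supplement. The documents do not support that, because of this check. What remains is that the veto is implied and not written, that 'and/or' leaves its pass condition open, and that the null rate runs from a few percent to nearly 100% depending on the reading.

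A reader might also infer that an inert supplement will usually yield a time point. That holds for 50 mediators. For 10 mediators and one dose the rate is about a third to a half. Summing counts over the three doses gives 71-74% with 10 mediators and 89-93% with 50, but the plan describes no such summing. Nor does the 9.3 rule always produce a winner, as step 4 shows.

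Finally, the synopsis calls the study exploratory, and picking the best candidate without a null gate is an accepted exploratory approach. That supports showing a ranking. It does not support reporting the top-ranked time point as a finding in a plan that sets a 5% level and 80% power and carries the selection into later trials.

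**Conclusion.** The concern holds in limited form. Neither selection rule can return 'none identified', and the white-cell check does not say that a named time point or dose is withdrawn. With no true effect, the 9.4 rule for one dose names a single time point in roughly 70-83% of trials with 50 mediators and roughly 35-54% with 10. These figures rest on two-sided tests, two time points and assumed correlations of 0 to 0.6; stronger correlation lowers them. They also assume no drift over the day. Because the rule has no placebo contrast, any such drift would count as change and could raise them. The 9.3 rule may name no single cell, but it requires no evidence of an effect when it does.

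**What to change.** Add to 9.3 and 9.4:

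> A time point and dose will be named as of interest only if the largest number of mediators showing a significant rise relative to the same participant's placebo cycle (baseline-adjusted change on supplement minus change on placebo, signed-rank test) in any dose-time cell exceeds its within-participant permutation distribution (four cycle labels shuffled within participant, all mediators and times kept together) at the 5% level. If this is not met, or if the Wilcoxon tests of white-cell function show no favourable change so that the mediators are classed as false positives, the report will state that no time point or dose was identified and will show the ranking as descriptive only.

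The same edit should settle whether 10 or 50 mediators are tested, and which white-cell readouts count and at what level.

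Two features of the wording matter.
- **The placebo contrast.** Three of the four cycles are active, so shuffling labels leaves plain pre/post rises in place. With a simulated 1 SD rise in all 50 mediators at every dose, a gate on pre/post rises fired in only 1-2% of trials, against 100% with the placebo contrast.
- **Permutation in place of a fixed minimum.** With 50 mediators and two times, requiring at least 7 significant results gives a null error of 2.3% if mediators are independent, but about 14% at correlation 0.3 and 21% at 0.6.

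With no effect, the permutation part of the gate fired in 2.4% (correlation 0) and 2.8% (correlation 0.3) of simulated trials (n = 33, 50 mediators, 250 trials each).

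The cost is a few sentences and a short program on data already planned, with no extra samples or participants. The downside is that a modest true effect may be reported as not identified, although the estimates and ranking are still shown.

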9. STATISTICAL CONSIDERATIONS

9.1 Primary Endpoint

The Primary endpoint of the study will be an increase in peripheral blood SPM levels that will be measured using established liquid chromatography tandem mass spectrometry based approach.

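### The 2–3 false positives in Sections 9.3 and 9.4 cover one dose at one time point, and Section 9.4 tests 10 mediators but counts errors for 50

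*Combined protocol and SAP*

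**What the plan says.** Section 9.4 states that the Wilcoxon matched-pairs signed rank test "will be used to analyse the pre and post values of 10 mediators" and white-cell function at 2 h and 4 h. Two sentences later it gives the error count: "At the 5% level of significance testing 50 mediators will result in at least 2-3 associations being falsely statistically significant". Section 9.3 says "Fifty mediators will be examined" and expects that "at the 5% level of statistical significance around 2-3 mediators will falsely be identified as having significant changes". In Section 9.3 the number 10 describes the published data behind the power calculation, not the panel to be tested.

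Section 9.4 selects the time point with the most mediators "statistically significantly different from their pre-test values at the 5% level of statistical significance". Section 9.3 goes on to choose a time point and dose for future trials by the greatest overall change in mediators and white-cell responses. No multiplicity correction is planned. Both sections instead send significant mediators to a white-cell function check, and treat them as false positives if no functional change is seen.

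The sample size of 33 is justified "with a power of 80% at the 5% level of statistical significance". The primary endpoint is "an increase in peripheral blood SPM levels", with no mediators named. The synopsis calls the study exploratory and says there will be no formal statistical analysis.

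**The concern.** The error count multiplies the significance level by the number of mediators and nothing else. The design also has two tested time points, three doses and a placebo, and the plan picks a best time point and dose from the results. A count that leaves these out understates how many mediators will look regulated by chance.

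The panel size is unsettled as well. The number of primary hypotheses differs fivefold between the test sentence and the error sentence of Section 9.4, and the endpoint definition does not settle it. At stake are the list of mediators reported as responding to fish oil and the time point and dose carried into later trials.

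**Working it through.** **Inputs**

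- Level per test: 5%, with no correction (Section 9.4). Sidedness is not stated.
- Panel: 10 (test sentence of 9.4) or 50 (error sentence of 9.4, and 9.3).
- Time points tested against pre-dose: 2 h and 4 h, after fatty acid and after placebo (9.3).
- Treatments: every participant receives three doses and placebo (8.3).
- Sample size: 33, for a threefold odds of an increase with 80% power (9.3).

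**The plan's own figure.** The expected number of false positives when every null is true is tests × level. For one dose at one time point, 50 × 0.05 = 2.5, which reproduces the stated 2–3.

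**The count over the planned comparisons.** Tests = mediators × time points × treatments; expected false positives = tests × 0.05.

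| Comparisons with pre-dose | 50 mediators | 10 mediators |
|---|---|---|
| One dose, one time point | 50 tests, 2.5 | 10 tests, 0.5 |
| Two time points, doses pooled | 100 tests, 5 | 20 tests, 1 |
| Two time points, three doses separately | 300 tests, 15 | 60 tests, 3 |
| Two time points, three doses and placebo | 400 tests, 20 | 80 tests, 4 |

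Correlation between mediators leaves these averages unchanged but widens their spread. If the tests are two-sided, about half of the false positives would be apparent increases: 7.5 of the 15. The 6 h and 24 h samples and the interim analysis mentioned in Section 8.3 are not counted.

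**Is 2–3 a minimum?** With 50 independent tests, P(0) = 0.95^50 = 0.077 and P(1) = 50 × 0.05 × 0.95^49 = 0.203. Together these give 0.28, so fewer than two false positives is a common result.

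**Effect of choosing the time point.** Within one dose, take two independent counts, each binomial with 50 tests at 0.05. The larger averages about 3.3 (200,000 simulated pairs), against 2.5 for a time point fixed in advance.

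**What the 80% refers to.** Threefold odds means P(increase) = 0.75. Noether's sign-test formula gives (1.960 + 0.842)² / (4 × 0.25²) = 31.4. Dividing by the relative efficiency 3/π gives 32.9, so 33. The exact two-sided sign test at n = 33 has 81.9% power. The stated size is therefore consistent with one mediator in one comparison at an unadjusted two-sided 5%. The source of the plan's formula is not available here, so this shows consistency only.

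**Can the white-cell check sort the list?** Under Section 8.7, phagocytosis and activation are measured on whole blood, so each sample gives one set of functional results whatever the number of mediators. A functional change at a given dose and time keeps every significant mediator there; no change rejects them all. The functional tests are themselves uncorrected, and the and/or wording leaves open which result decides.

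**The case against.** The plan does not hide the problem. It says that false positives will occur, and it names a second step for dealing with them. A reader might infer that the plan goes without correction because it regards two or three false positives as few enough to accept. The documents do not say this: the count serves as a warning, and the stated response is the functional check. That part of the defence stands, although the check cannot do the job given to it.

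A reader might also take 15 as the plan's own count. It is not, because the plan never states its number of tests. Fifteen requires 50 mediators, two time points, separate testing of three doses, placebo left out and every null true. With the 10 mediators of the test sentence, the same scheme gives 3, in line with the stated figure. The objection limits the claim to a conditional range, but it does not rescue the sentence, which is explicitly about 50.

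Two further inferences go too far. Taking the largest significant count over all six dose-by-time cells would model a rule the plan does not state: the count of significant mediators selects the time point only, and Section 9.3 chooses dose and time by overall change. Quoting power at a Bonferroni level for 50 mediators would not show the cost of false discovery rate control, which is a different procedure.

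Finally, the study is described as exploratory, which weakens any call for confirmatory error control. That stands in part. But Section 9.4 sets significance tests and decision rules despite the synopsis, and the plan uses their results to choose a time point.

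**Conclusion.** The concern holds in this form. The 2–3 figure is correct arithmetic for one dose at one time point but too low for the comparisons the plan describes on a 50-mediator panel: 5, 15 or 20, depending on whether doses are pooled, tested separately or joined by placebo. All three assume that every null is true. If the panel is 10, separate dose testing gives 3, or 4 with placebo, and the sentence about 50 is then wrong on panel size instead. Calling the figure a minimum is wrong under either panel; the 28% and the 3.3 rest on 50 independent tests.

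The 10-versus-50 conflict within Section 9.4 needs no assumption. The white-cell check does not replace error control. The documents do not support saying that the plan relies on the small count as its reason for not correcting.

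**What to change.** 1. Use one panel size in Sections 9.3 and 9.4, and list the mediators.
2. State the number of mediator × dose × time tests, including whether doses are pooled and whether placebo is tested against baseline. Give the expected false positives for that number.
3. Delete *at least*.
4. Apply Benjamini–Hochberg false discovery rate control over the stated set of tests. Alternatively, if the results are to stay exploratory as the synopsis says, report them without significance claims and align Section 9.4 with the synopsis.
5. Describe the white-cell results as supporting evidence for a dose and time, not as a filter that identifies false-positive mediators.
6. Label the 80% as power for one mediator in one unadjusted comparison.

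The cost is SAP wording and a few lines of analysis code, with no change to conduct. The stated error count and power will look less favourable.
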